9.2.2. Post-Study adverse events and serious adverse events

A post-study AE/SAE is defined as any event that occurs outside of the AE/SAE reporting period defined in [Table 23](#). Investigators are not obligated to actively seek AEs or SAEs in former study participants. However, if the investigator learns of any SAE at any time after a subject has been discharged from the study, and he/she considers the event reasonably related to the investigational vaccine/product, the investigator will promptly notify the Study Contact for Reporting SAEs.

9.2.3. Evaluation of adverse events and serious adverse events**9.2.3.1. Active questioning to detect adverse events and serious adverse events**

As a consistent method of collecting AEs, the subject should be asked a non-leading question such as: *“Have you felt different in any way since receiving the vaccine or since the previous visit?”*

When an AE/SAE occurs, it is the responsibility of the investigator to review all documentation (e.g. hospital progress notes, laboratory and diagnostics reports) relative to the event. The investigator will then record all relevant information regarding an AE/SAE in the eCRF. The investigator is not allowed to send photocopies of the subject's medical records to GSK Biologicals instead of appropriately completing the eCRF. However, there may be instances when copies of medical records for certain cases are requested by GSK Biologicals. In this instance, all subject identifiers will be blinded on the copies of the medical records prior to submission to GSK Biologicals.

The investigator will attempt to establish a diagnosis pertaining to the event based on signs, symptoms, and/or other clinical information. In such cases, the diagnosis should be documented as the AE/SAE and not the individual signs/symptoms.

9.2.3.2. Assessment of adverse events**9.2.3.2.1. Assessment of intensity**

The intensity of the following solicited AEs will be assessed as described:

Table 24 Intensity scales for solicited symptoms in adults (Amended: 29 January 2014)

Adults		
Adverse Event	Intensity grade	Parameter
Pain at injection site	0	None
	1	Mild: Any pain neither interfering with nor preventing normal every day activities.
	2	Moderate: Painful when limb is moved and interferes with every day activities.
	3	Severe: Significant pain at rest. Prevents normal every day activities.
Redness at injection site		Record greatest surface diameter in mm
Swelling at injection site		Record greatest surface diameter in mm
Fever*		Record temperature in °C/F
Headache	0	Normal
	1	Mild: Headache that is easily tolerated
	2	Moderate: Headache that interferes with normal activity
	3	Severe: Headache that prevents normal activity
Fatigue	0	Normal
	1	Mild: Fatigue that is easily tolerated
	2	Moderate: Fatigue that interferes with normal activity
	3	Severe: Fatigue that prevents normal activity
Respiratory symptoms (cough, blood in sputum, purulent sputum, shortness of breath or difficulties breathing, chestwall pain)	0	No symptoms
	1	Mild: symptoms that are easily tolerated
	2	Moderate: symptoms that interfere with normal activity
	3	Severe: symptoms that prevent normal activity
Malaise	0	Normal
	1	Malaise that is easily tolerated
	2	Malaise that interferes with normal activity
	3	Malaise that prevents normal activity
Myalgia	0	Normal
	1	Myalgia that is easily tolerated
	2	Myalgia that interferes with normal activity
	3	Myalgia that prevents normal activity

*Fever is defined as temperature $\geq 37.5^{\circ}\text{C} / 99.5^{\circ}\text{F}$ for oral, axillary or tympanic route, or $\geq 38.0^{\circ}\text{C} / 100.4^{\circ}\text{F}$ for rectal route. The preferred route for recording temperature in this study will be axillary.

The investigator will assess the maximum intensity that occurred over the duration of the event for all unsolicited AEs (including SAEs) recorded during the study. The assessment will be based on the investigator's clinical judgement.

The intensity should be assigned to one of the following categories:

1 (mild) = An AE which is easily tolerated by the subject, causing minimal discomfort and not interfering with everyday activities.

2 (moderate) = An AE which is sufficiently discomforting to interfere with normal everyday activities.

3 (severe) = An AE which prevents normal, everyday activities

In adults, such an AE would, for example, prevent attendance at work and would necessitate the administration of corrective therapy.

An AE that is assessed as Grade 3 (severe) should not be confused with a SAE. Grade 3 is a category used for rating the intensity of an event; and both AEs and SAEs can be assessed as Grade 3. An event is defined as 'serious' when it meets one of the pre-defined outcomes as described in Section 9.1.2.

9.2.3.2.2. Assessment of causality

The investigator is obligated to assess the relationship between investigational vaccine/product and the occurrence of each AE/SAE. The investigator will use clinical judgement to determine the relationship. Alternative plausible causes, such as natural history of the underlying diseases, concomitant therapy, other risk factors, and the temporal relationship of the event to the investigational vaccine/product will be considered and investigated. The investigator will also consult the IB to determine his/her assessment.

There may be situations when a SAE has occurred and the investigator has minimal information to include in the initial report to GSK Biologicals. However, it is very important that the investigator always makes an assessment of causality for every event prior to submission of the SAE report to GSK Biologicals. The investigator may change his/her opinion of causality in light of follow-up information and update the SAE information accordingly. The causality assessment is one of the criteria used when determining regulatory reporting requirements.

In case of concomitant administration of multiple vaccines, it may not be possible to determine the causal relationship of general AEs to the individual vaccines administered. The investigator should, therefore, assess whether the AE could be causally related to vaccination rather than to the individual vaccines.

All solicited local (injection site) reactions will be considered causally related to vaccination. Causality of all other AEs should be assessed by the investigator using the following question:

"Is there a reasonable possibility that the AE may have been caused by the investigational vaccine/product?"

YES: There is a reasonable possibility that the vaccine(s) contributed to the AE.

NO: There is no reasonable possibility that the AE is causally related to the administration of the study vaccine(s). There are other, more likely causes and administration of the study vaccine(s) is not suspected to have contributed to the AE.

If an event meets the criteria to be determined as 'serious' (see Section 9.1.2), additional examinations/tests will be performed by the investigator in order to determine ALL possible contributing factors for each SAE.

Possible contributing factors include:

- Medical history.
- Other medication.
- Protocol required procedure.
- Other procedure not required by the protocol.
- Lack of efficacy of the vaccines, if applicable.
- Erroneous administration.
- Other cause (specify).

9.2.3.3. Assessment of outcomes

The investigator will assess the outcome of all unsolicited AEs (including SAEs) recorded during the study as:

- Recovered/resolved.
- Recovering/resolving.
- Not recovered/not resolved.
- Recovered with sequelae/resolved with sequelae.
- Fatal (SAEs only).

9.2.3.4. Medically attended visits

For each solicited and unsolicited symptom the subject experiences, the subject will be asked if he/she received medical attention defined as hospitalisation, or an otherwise unscheduled visit to or from medical personnel for any reason, including emergency room visits. This information will be recorded in the eCRF.

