11.9. Analysis of safety

The primary analysis will be based on the TVC for analysis of safety. If, in any vaccine group, the percentage of vaccinated subjects excluded from the ATP cohort for analysis of safety is 5% or more, a second analysis based on the ATP cohort for analysis of safety will be performed to complement the TVC analysis.

Analyses of solicited (local and general) AEs and clinical laboratory observations will be performed for the safety and immune sub-cohort only. (Amended: 29 January 2014)

The following analyses will be performed:

- The percentage of subjects with at least one local AE (solicited and/or unsolicited), with at least one general AE (solicited and/or unsolicited) and with any AE during the solicited follow-up period will be tabulated with exact 95% CI after each vaccine dose and overall. The percentage of doses followed by at least one local AE (solicited and/or unsolicited), by at least one general AE (solicited and/or unsolicited) and by any AE will be tabulated, overall vaccination course, with exact 95% CI.
- The percentage of subjects reporting each individual solicited local and general AE during the solicited follow-up period will be tabulated with exact 95% CI. The percentage of doses, followed by each individual solicited local and general AE will be tabulated, overall vaccination course, with exact 95% CI.
- Injection site swelling and redness will be analysed using a 3-grade evaluation system [0 mm **to 20 mm** (grade 0); **≥20 to 50 mm** (grade 1); **> 50 to 100 mm** (grade 2); **> 100 mm** (grade 3)]. **(Amended: 29 January 2014)**
- Occurrence of fever will be reported per 0.5°C cumulative increments. Duration and prevalence of fever will be presented. Fever will also be analysed using a 3-grade evaluation system [**< 37.5°C** (grade 0); **≥ 37.5°C but ≤ 38.0°C** (grade 1); **> 38.0°C but ≤ 39.5°C** (grade 2); **> 39.5°C** (grade 3)].
- The same tabulation will be performed for grade 3 AEs and for AEs with relationship to vaccination.
- The percentage of subjects with at least one report of unsolicited AE classified by the Medical Dictionary for Regulatory Activities (MedDRA) and reported up to 30 days after vaccination will be tabulated with exact 95% CI. The same tabulation will be performed for grade 3 unsolicited AEs and for unsolicited AEs with a relationship to vaccination.
- The percentage of subjects reporting AEs resulting in a medically attended visit will also be tabulated.

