11.10.4. All symptoms

This analysis will be performed in the safety and immunogenicity sub-cohort.

- The percentage of subjects with at least one local AE (solicited and/or unsolicited), with at least one general AE (solicited and/or unsolicited) and with any AE during the solicited follow-up period (Day 0 to Day 6) will be tabulated by treatment group with exact 95% CI after each vaccine injection and overall.
- The percentage of doses followed by at least one local AE (solicited and/or unsolicited), by at least one general AE (solicited and/or unsolicited) and by any AE will be tabulated by treatment group, overall vaccination course, with exact 95% CI.

The same tabulations will be done for grade 3 AEs and for AEs causally related to vaccination.

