11.11. Solicited symptoms

The analysis of solicited symptoms will be performed in the safety and immunogenicity sub-cohort.

The number and percentage of subjects reporting each individual solicited local (any, grade ≥ 2 , grade 3) and general (any, related to vaccination, grade ≥ 2 , grade 3, grade ≥ 2 related to vaccination and grade 3 related to vaccination) AE during the solicited follow-up period will be tabulated by treatment group with exact 95% CI.

The number and percentage of doses followed by each individual solicited local (any, grade ≥ 2 and grade 3) and general (any, related to vaccination, grade ≥ 2 , grade 3, grade ≥ 2 related to vaccination and grade 3 related to vaccination) AE will be tabulated by treatment group, overall vaccination course, with exact 95% CI.

The percentage of doses followed by each individual solicited local and general (any, grade 3) AE will be presented in a bar chart by treatment group, overall vaccination course (2 doses combined), with exact 95% CI.

Occurrence of fever will also be reported per 0.5°C cumulative increments.

The number of days with a solicited symptom during the solicited follow-up period will also be presented by treatment group. The same tabulations will be done for grade 3 AEs and for general AEs with relationship to vaccination.

The number of days with a solicited symptom during the solicited follow-up period and beyond will also be presented by treatment group. The same tabulations will be done for grade 3 AEs and for general AEs with relationship to vaccination.

The number of solicited local and general symptoms ongoing beyond the 7-day post-vaccination period is given by treatment group as well as descriptive statistics (Q1, median, Q3) concerning the time-to-resolution (in days from the last day of the follow-up period to the last day the symptom was observed).

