11.13. Unsolicited symptoms

The proportion of subjects/doses with at least one report of unsolicited AE classified by the Medical Dictionary for Regulatory Activities (MedDRA) reported during the 30-day follow-up period (Days 0 to 29) will be tabulated with exact 95% CI by treatment group.

The same tabulations will be done for grade 3 AEs, AEs related to vaccination, grade 3 events related to vaccination and AEs resulting in a medically attended visit.

As only the subjects part of the safety and immunogenicity sub-cohort have a diary card to collect the solicited AEs, those symptoms (redness, swelling, pain at injection site, fever, headache, respiratory symptoms, malaise, myalgia)) reported for the other subjects were recorded in the Case Report Form (CRF) section on unsolicited symptoms.

Therefore to assess the impact of this situation, the following analyses will be proposed:

- The same analysis will be produced for the subjects with diary cards (part of the safety and immunogenicity sub-cohort).
- The proportion of subjects/doses with at least one report of unsolicited AE classified by MedDRA reported during the 7-day follow-up period (Days 0 to 7) will be tabulated with exact 95% CI by treatment group. Idem for grade 3 AEs, AEs related to vaccination, grade 3 events related to vaccination.
- The proportion of subjects/doses with at least one report of unsolicited AE classified by MedDRA reported after the 7-day follow-up period (Days 7 to 29) will be tabulated with exact 95% CI by treatment group. Idem for grade 3 AEs, AEs related to vaccination, grade 3 events related to vaccination.

The proportion of subjects with at least one report of unsolicited AE associated to the respiratory system classified by the MedDRA reported during the 90-day post-vaccination follow-up period (on or after Day 0 to Day 89) will be tabulated with exact 95% CI by treatment group, for all subjects in the TVC population.

The same tabulation will be done for, grade 2 or 3 AE associated to the respiratory system, grade 3 AE associated to the respiratory system, AE associated to the respiratory system related to vaccination, grade 2 or 3 AE associated to the respiratory system related to vaccination and grade 3 AE associated to the respiratory system related to vaccination.

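### The SAP tabulates medically attended AEs for unsolicited symptoms only, although the protocol collects medical attention for solicited symptoms too and plans the percentage for AEs in general

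*Protocol*

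**What the plan says.** **Collection.** Protocol 9.2.3.4 reads: "For each solicited and unsolicited symptom the subject experiences, the subject will be asked if he/she received medical attention". Medical attention is "defined as hospitalisation, or an otherwise unscheduled visit to or from medical personnel for any reason, including emergency room visits". The section ends: "This information will be recorded in the eCRF".

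**Planned analysis.** Protocol 11.9 has a separate bullet: "The percentage of subjects reporting AEs resulting in a medically attended visit will also be tabulated".

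**SAP.**
- 11.13 (unsolicited symptoms) repeats its tabulation for several categories, ending with "grade 3 events related to vaccination and AEs resulting in a medically attended visit".
- 11.10.4 (all symptoms, solicited and/or unsolicited, in the sub-cohort) says only: "The same tabulations will be done for grade 3 AEs and for AEs causally related to vaccination".
- 11.11 (solicited symptoms) tabulates each reaction by any, grade 2 or higher and grade 3, with relationship added for general symptoms. It has no medically attended category.
- 11.12 (large swelling reaction) gives counts, duration and size.
- 11.13 also explains that only sub-cohort subjects have a diary card for solicited AEs, and that the same kinds of symptom "reported for the other subjects were recorded in the Case Report Form (CRF) section on unsolicited symptoms".
- Section 14 (changes from planned analyses) does not mention a restriction of the medically attended tabulation.

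**The concern.** Whether a reaction led someone to seek care is a useful descriptor of reactogenicity, and the protocol takes the trouble to ask about it for solicited symptoms. The sub-cohort is the only group in which reactions are actively solicited, yet it is there that the SAP text makes no use of the answer for solicited symptoms.

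There is a second consequence. A fever on Day 3 that led to a clinic visit counts as a medically attended unsolicited AE if the subject is outside the sub-cohort. Inside the sub-cohort it is a solicited AE and does not count. One TVC percentage would therefore combine subjects classified under two rules. A reader of the study report would have no way to see this, because the restriction is not recorded as a change from the protocol.

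**Working it through.** The documents give no figure for this point, so there is nothing to reproduce. The check is a comparison of sections, followed by a bound under a stated assumption.

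**Step 1: what the protocol commits to.** Section 9.2.3.4 covers solicited and unsolicited symptoms. The 11.9 bullet refers to AEs without qualification, whereas the bullet before it specifies unsolicited AEs. Section 9.1.1 treats solicited AEs as AEs. The unrestricted reading is the natural one.

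**Step 2: what the SAP text delivers.**

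| SAP section | Medically attended category |
|---|---|
| 11.10.4 All symptoms | No |
| 11.11 Solicited symptoms | No |
| 11.12 Large swelling reaction | No |
| 11.13 Unsolicited symptoms | Yes |
| 11.14 Serious adverse events | No (all SAEs are tabulated) |

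**Step 3: whether the SAP's own checks close the gap.** SAP 11.13 recognises that recording differs between the sub-cohort and other subjects, and adds two kinds of analysis. The repeat in sub-cohort subjects still covers unsolicited AEs only. The early and late splits of the 30-day period are repeated for grade 3, related, and grade 3 related AEs, not for medically attended ones. Neither restores the solicited reactions.

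**Step 4: which reactions are affected.**
- Hospitalisation is a seriousness criterion (protocol 9.1.2), so hospitalised reactions enter the SAE tables of SAP 11.14.
- A solicited-type symptom with onset after the solicited window is unsolicited by the protocol glossary and falls under 11.13.
- What remains is chiefly non-hospital visits for Day 0-6 reactions in the sub-cohort.

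**Step 5: a bound on the size.**
- Inputs from protocol 5.1 and 6.2: sub-cohort about 450 of 3506; per arm about 225 of 1753.
- Sub-cohort share: 450 / 3506 = 12.8%; per arm, 225 / 1753 = 12.8%.
- Assumption, not in the documents: 2% to 5% of vaccine recipients seek care for a Day 0-6 reaction.
- Vaccine-arm sub-cohort subjects affected: 225 × 0.02 = 4.5 and 225 × 0.05 = 11.25, so about 5 to 11.
- Shortfall in the vaccine-arm TVC percentage: 0.128 × 2% = 0.26 points and 0.128 × 5% = 0.64 points.

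Given the assumed rate, these are upper bounds. The measure counts subjects, so anyone who also had an attended unsolicited AE in the same period is already included.

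**The case against.** Five arguments can be made for the plan.

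1. *The protocol bullet may have been meant for unsolicited AEs.* It directly follows the unsolicited-AE bullet, the bullets on solicited AEs do not mention medical attention, and SAP 11.13 puts the item in the same place. This reading is possible. The bullet does not state it, though, and it would leave an item collected for solicited symptoms with no planned use.

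2. *The reactions are not hidden.* This stands. A reader might infer that reactions which sent sub-cohort subjects to care appear in no table. The documents do not support that: the reactions are in 11.10.4 and 11.11, large swelling has its own tables, and hospitalised reactions are in the SAE tables. Only the medically attended status is missing.

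3. *The table shells are in a separate Table and Figures List.* It was not among the documents, so the point can be made only about the SAP text.

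4. *The item is an imperfect measure.* It counts unscheduled visits for any reason, and protocol 9.1.1 tells subjects with a large injection site reaction to come to the investigator's office. For that reaction it partly reflects an instruction. This limits interpretation, but it applies equally to subjects outside the sub-cohort, whose visits are counted.

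5. *Mixing solicited and unsolicited AEs under 11.13 would blur ascertainment.* This is fair, and is why the fix keeps the unsolicited-only figure and adds a second one beside it.

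**Conclusion.** The point holds in a limited form. The protocol collects medical attention for solicited symptoms and, on its natural reading, plans a percentage covering all AEs. The SAP text plans it for unsolicited AEs only and does not record the narrowing. The TVC figure in 11.13 consequently follows one rule inside the sub-cohort and another outside it, and leaves out attended solicited reactions in about 450 subjects.

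The size of the shortfall cannot be derived from the documents. Under the assumed 2% to 5% care-seeking rate it is at most about 0.26 to 0.64 percentage points in the vaccine arm.

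A reader might go further and conclude that the difference between arms is diluted by 12.8%. That would require equal ascertainment inside and outside the sub-cohort, which the design does not give: only the sub-cohort has active solicitation and the Day 7 and Day 37 visits. The omission may fall more heavily on the vaccine arm, since SAP 11.12 expects large swelling to occur mainly there, but the documents do not quantify this.

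The output is descriptive. Efficacy, the type I error and the safety holding rules are unaffected.

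**What to change.** - In SAP 11.10.4 and 11.11, add a medically attended category for the sub-cohort, by arm with exact 95% CI.
- Beside the unsolicited-only figure in 11.13, report the overall TVC percentage of subjects with any medically attended AE, solicited or unsolicited, in Days 0-29, by arm with exact 95% CI.
- If the restriction to unsolicited AEs was intended, state it and the reason in section 14. Protocol 11.11 in any case requires changes from the planned analysis to be described and justified in the final report.

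The cost is a short SAP edit and one or two extra table rows from an existing eCRF field. No new data collection is needed. A footnote should say that solicitation was active only in the sub-cohort, so that the overall percentage is read with that difference in mind.

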9.3. Reporting of serious adverse events, pregnancies, and other events

9.3.1. Prompt reporting of serious adverse events, pregnancies, and other events to GSK Biologicals

SAEs that occur in the time period defined in Section 9.2.1 will be reported promptly to GSK within the timeframes described in Table 25, once the investigator determines that the event meets the protocol definition of a SAE.

Pregnancies that occur in the time period defined in Section 9.2.1 will be reported promptly to GSK within the timeframes described in Table 25, once the investigator becomes aware of the pregnancy.

pIMDs that occur in the time period defined in Section 9.2.1 will be reported promptly to GSK within the timeframes described in Table 25, once the investigator becomes aware of the pIMD.

Table 25 Timeframes for submitting serious adverse event, pregnancy and other events reports to GSK Biologicals

Type of Event	Initial Reports		Follow-up of Relevant Information on a Previous Report	
	Timeframe	Documents	Timeframe	Documents
SAEs	24 hours*	Electronic SAE report	24 hours*	Electronic SAE report
Pregnancies	2 weeks*	Electronic pregnancy report	2 weeks*	Electronic pregnancy report
pIMDs	24 hours**	Electronic SAE report	24 hours*	Electronic SAE report

* Timeframe allowed after receipt or awareness of the information.

**Timeframe allowed after the diagnosis is established and known to the investigator.

9.3.2. Contact information for reporting serious adverse events and other events to GSK Biologicals

Study Contact for Reporting SAEs
Back-up Study Contact for Reporting SAEs
24/24 hour and 7/7 day availability:
GSK Biologicals Clinical Safety & Pharmacovigilance
Fax: PPD [REDACTED] or PPD [REDACTED]

